10.3 Statistical Analyses

The statistical analysis plan (SAP) will be developed and finalized before the first database lock for formal interim efficacy analysis, and will describe the selection of participants to be included in the analyses, and procedures for accounting for missing, unused, and spurious data. Below is a summary of planned statistical analyses of the primary and secondary endpoints.

A description of the participant population will be included in a statistical output report, including subgroups of age, gender and race.

10.3.1 Efficacy Analyses

10.3.1.1 Primary Endpoint Analysis

The primary endpoint is RFS. The primary endpoint of RFS will be programmatically determined based on the disease recurrence date provided by the investigator and is defined as the time between the date of randomization and the date of first recurrence (local, regional or distant metastasis), new primary melanoma (including melanoma in situ), or death (whatever the cause), whichever occurs first. For participants who remain alive and whose disease has not recurred or did not die, RFS will be censored on the date of last evaluable disease assessment. For those participants who remained alive and had no recorded post-randomization tumor assessment, RFS will be censored on the day of randomization. Censoring rules for the primary analysis of RFS are presented in Table 10.3.1.1-1.

| Situation | Date of Event or Censoring | Outcome |
|--|---|----------|
| Recurrence (local, regional, distant, new primary melanoma (including melanoma in situ)) | Date of first recurrence | Event |
| Death without recurrence | Date of death | Event |
| No baseline disease assessment | Date of randomization | Censored |
| No on-study disease assessments and no death | Date of randomization | Censored |
| No recurrence and no death | Date of last evaluable disease assessment | Censored |
| New anticancer therapy, tumor-directed radiotherapy, or tumor-directed surgery received without recurrence reported prior to or on the same day of disease assessment | Date of last evaluable disease assessment prior to or on the same date of initiation of subsequent therapy | Censored |
| Second non-melanoma primary cancer reported prior or on the same day of disease assessment | Date of last evaluable disease assessment prior to or on the same date of diagnosis of second non- melanoma primary cancer | Censored |

Table 10.3.1.1-1: Censoring Scheme for Primary Definition of RFS

RFS distributions will be compared between treatment groups (nivolumab vs placebo) using a twosided log-rank test stratified AJCC T-Stage at Screening at the overall significance level of 5% (two-sided) in all randomized participants.

The HR and corresponding 100x (1-adjusted α)% confidence intervals (CIs) will be estimated using a Cox proportional hazards model, with treatment group as a single covariate, stratified by the above factor.

RFS curves will be estimated using Kaplan-Meier (KM) product-limit methodology. Median RFS with two-sided 95% CIs using the log-log transformation will be computed. In addition, RFS rates at 6, 12, 18, 24, 30, and 36 months (and yearly after depending on follow-up) with two-sided 95% CIs using the log-log transformation will be computed.

The proportional hazards assumption will be assessed at the time of analysis and appropriate methods will be employed in case of non-proportional hazards.

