 - i) Participants with equivocal lymph nodes on imaging (≥ 10 mm and < 15 mm in a short axis) may be eligible if confirmation with histology/cytology is available. If risk of biopsy is too high or biopsy is not feasible, two sequential CT or MRI scans (as listed above) should be available and showing no progressive and measurable (lymph nodes ≥ 15 mm in short axis) disease or PET/CT demonstrating no FDG uptake. The second scan should occur at least 4 weeks after the initial scan. Participants with incidental findings (eg, indeterminate nodules noted on imaging) reported during screening may be eligible if confirmation of disease-free status can be documented by histology/cytology, imaging studies, or in certain situations by discussing with the Medical Monitor or designee. Note: Participants who have had a history of metastatic melanoma and have had their metastatic melanoma resected are not eligible.

- e) The complete set of baseline images must be available before randomization.
- f) Participant has not been previously treated for melanoma beyond complete surgical resection of the melanoma lesion.
- g) Participant has recovered adequately from toxicity and/or complications from surgery prior to study start.

- h) ECOG performance status of 0 or 1 at the time of enrollment (Appendix 6)
- i) Tumor tissue from the primary diagnostic biopsy (minimum of 15 unstained slides, preferably freshly cut, or 1 FFPE block to contain sufficient tissue for at least 15 sections) must be shipped to the central laboratory prior to randomization (see Section 9.8.2 for details). If the required tumor tissue content cannot be provided, the eligibility should be discussed with the Medical Monitor or designee.
- j) Participants must be able and willing to comply with the study visit schedule and study procedures.
- 3) Age and Reproductive Status
 - a) Males and Females, ≥ 12 years of age
 - i) Except: where local regulations and/or institutional policies do not allow for participants < 18 years of age (pediatric population) to participate. For those sites, the eligible participant population is ≥ 18 years of age

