10.3.1.2 Secondary Endpoint Analyses

Overall Survival (OS)

OS is defined as the time between the date of randomization and the date of death. For participants without documentation of death, OS will be censored on the last date the participant was known to be alive. OS will be followed continuously while participants are on the study drug and every 12 weeks via in-person or phone contact after participants discontinue the study drug.

OS distributions will be compared in hierarchical testing order (order defined in Section 10.3.4) between treatment groups (nivolumab vs placebo) using a two-sided log-rank test stratified by AJCC T-Stage at Screening at the overall significance level of 5% (two-sided) in all randomized

participants. The hazard ratio and corresponding two-sided 100x (1-adjusted α)% CIs will be estimated using a Cox proportional hazards model, with treatment group as a single covariate, stratified by the above factors.

OS curves will be estimated using Kaplan-Meier (KM) product-limit methodology. Median OS with two-sided 95% CIs using the log-log transformation will be computed. In addition, OS rates at 6, 12, 18, 24, 30 and 36 months (and yearly after depending on follow-up) with two-sided 95% CIs using the log-log transformation will be computed.

Distant Metastasis-Free Survival (DMFS)

DMFS is defined as the time between the date of randomization and the date of first distant metastasis or date of death (whatever the cause), whichever occurs first.

Censoring rules for the analysis of DMFS are presented in Table 10.3.1.2-1.

Table 10.3.1.2-1:Censoring Scheme for Primary Definition of DMFS

| Situation | Date of Event or Censoring | Outcome |
|--|---|----------|
| Distant metastasis | Date of first distant metastasis | Event |
| Death without distant metastasis | Date of death | Event |
| No baseline disease assessment | Date of randomization | Censored |
| No on-study disease assessments and no death | Date of randomization | Censored |
| No distant metastasis and no death | Date of last evaluable disease assessment | Censored |

DMFS will be analyzed using similar analyses methods as for RFS. No multiplicity adjustment will be applied.

Investigator-Assessed Outcomes on Next-Line Therapies

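### The no-baseline-assessment row in the RFS and DMFS censoring tables has no exception for a later death or recurrence and, read literally, contradicts the endpoint definitions

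*Combined protocol and SAP*

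**What the plan says.** Section 10.3.1.1 measures RFS from randomization to first recurrence, "new primary melanoma (including melanoma in situ), or death (whatever the cause), whichever occurs first". The text above Table 10.3.1.1-1 then says when a participant is censored at day 0: "For those participants who remained alive and had no recorded post-randomization tumor assessment, RFS will be censored on the day of randomization". The test is made "at the overall significance level of 5% (two-sided) in all randomized participants".

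Three rows of the table matter here:

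- an event row: "Death without recurrence | Date of death | Event"
- the row at issue: "No baseline disease assessment | Date of randomization | Censored"
- the row directly below it: "No on-study disease assessments and no death | Date of randomization | Censored"

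Section 10.3.1.2 defines the DMFS endpoint as the "date of first distant metastasis or date of death (whatever the cause), whichever occurs first". Table 10.3.1.2-1 repeats the no-baseline row without a condition, again directly above a row that exempts deaths. Neither table gives an order of precedence among rows.

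Section 6.1.1 bears on how often the row could apply: "The complete set of baseline images must be available before randomization".

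**The concern.** A participant with no baseline assessment who later dies or recurs meets two rows at once: an event row, and a censoring row that sets follow-up to zero. The plan does not say which applies. If the censoring row is programmed as it stands, an event that the endpoint definition counts is left out of the primary analysis, and the participant contributes nothing to a comparison meant to cover everyone randomized. OS has no such row, so the same death would count for OS and vanish from RFS and DMFS.

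At stake are the agreement of the primary endpoint with its own definition and the count of RFS events that triggers the interim and final analyses. For DMFS, which is tested without multiplicity adjustment, the stake is the reported estimate.

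**Working it through.** **Design figures.** The point disputes no number, but the event counts fix the boundaries, so these were checked first. Inputs from Sections 10.1.1 and 10.3.4: 123 and 154 RFS events, overall two-sided alpha 0.05, Lan-DeMets spending of O'Brien-Fleming type. The information fraction is t = 123/154 = 0.799. The one-sided alpha spent at the interim is 2[1 − Φ(z₀.₉₈₇₅/√t)] = 2[1 − Φ(2.241/0.894)] = 0.0121, which is 0.0243 two-sided (z = 2.253). Solving the bivariate normal for the final bound gives z = 2.025, or 0.0429 two-sided. The plan states 0.024 and 0.043, so both reproduce.

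**The rows against the definitions.** Take four randomized participants, none with a baseline assessment, under RFS:

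| Later course | Definition and RFS text | Other rows of the table | No-baseline row, literally |
|---|---|---|---|
| A. Dies without recurrence | Event at death | Event at death | Censored at day 0 |
| B. Recorded recurrence | Event at recurrence | Event at recurrence | Censored at day 0 |
| C. Event-free, with on-study assessments | Censored at last evaluable assessment | Censored at last evaluable assessment | Censored at day 0 |
| D. Alive, no on-study assessment | Censored at day 0 | Censored at day 0 | Censored at day 0 |

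Only in D do all sources agree, and D is already covered by the row below. In A and B an observed event is lost; in C only follow-up time is lost. For DMFS the same holds with distant metastasis in place of recurrence, except that Section 10.3.1.2 has no separate text limiting day-0 censoring, so the conflict there is with the definition, the event rows and the neighbouring row.

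**Is the missing condition deliberate?** The next two rows of each table carry their own event exclusions; this one does not. A death needs no baseline scan to be established. Section 9.1.2.4 also allows recurrence to be declared on pathology alone for certain lesions. Nothing in the section explains why such events should be dropped.

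**Size.** The documents give no count of participants without a baseline assessment. Assuming, purely for illustration, 1 to 5 uncounted RFS events, the share is 1/154 = 0.6% to 5/154 = 3.2% of the final target, or 1/123 = 0.8% to 5/123 = 4.1% of the interim target. Since the analyses wait for counted events, the 154th counted event would then be the 155th to 159th that occurred.

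**The case against.** The strongest reply has three parts.

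First, the event rows stand at the top of each table and are just as unconditional, so a programmer who applied them first would keep every event. That is a possible reading, and it is why the point is confined to the literal reading and the missing precedence. A reader might infer that events will certainly be discarded; the documents do not establish that. Nor do they establish the opposite. The RFS rows for new anticancer therapy and for a second non-melanoma cancer censor at a date before later events, so event rows do not win everywhere in that table.

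Second, a baseline requirement has some rationale for recurrence. Section 9.1.2.3 defines recurrence by new lesions, and Table 9.1.2.2-1 relies on new lesions or on nodes that were previously normal or equivocal. Without a baseline, newness on imaging is hard to show. This stands for imaging-based recurrence and distant metastasis, and it is why a no-death condition is the minimum fix. It does not apply to deaths, and it does not remove the conflict between the row and the RFS text for recorded recurrences.

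Third, the situation should be rare. Complete baseline images are required before randomization, and Section 9 bars waivers. This also stands and limits the size. Section 10.3 calls itself a summary and leaves missing-data procedures to the SAP, but no text in the documents supplied settles this row.

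A reader might also infer that a late or unreadable scan could be ruled as no baseline once the outcome is known. The row speaks only of no assessment, and Section 10.3.1.1 has RFS derived programmatically, so the text does not support that step.

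**Conclusion.** The row is wrong as written. Taken literally it contradicts the RFS and DMFS definitions, the RFS text on day-0 censoring and the pattern of the neighbouring rows, and no precedence rule rescues it. The contradiction is plainest for deaths; for recorded recurrences it rests on the definition and the RFS text, with the baseline rationale as a partial counterweight.

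The expected effect is small. This rests on the entry requirement for baseline images being followed; the number of exceptions is unknown. In an event-driven analysis the main consequence would be later triggers at 123 and 154 counted events. A reader might go further and infer a loss of power or a result tipped across the boundary. The documents do not support either: power would fall only if missing events were not replaced, and tipping a result would need several losses in one arm with the estimate already at the critical value. Neither is claimed.

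**What to change.** At minimum, add *and no death* to the no-baseline row in Tables 10.3.1.1-1 and 10.3.1.2-1. Preferably, to match the definitions and the RFS text, add *and no recurrence and no death* for RFS (with recurrence including new primary melanoma, as in the table's first row) and *and no distant metastasis and no death* for DMFS.

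Alternatively, state that the event rows take precedence over this row. The statement should be limited to this row, because a general rule would also alter the new-therapy and second-cancer rows. With either wording, it is worth adding that event-free participants who do have on-study assessments are censored at the last evaluable one, as the RFS text already provides.

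The cost is one line in each of two tables, settled before the relevant database lock. It needs no new data and changes no alpha, event target or design power. There is one small downside: disease present but undetected at entry could be counted as an early event, equally in both arms in expectation.

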10.3.1.2 Secondary Endpoint Analyses

Overall Survival (OS)

OS is defined as the time between the date of randomization and the date of death. For participants without documentation of death, OS will be censored on the last date the participant was known to be alive. OS will be followed continuously while participants are on the study drug and every 12 weeks via in-person or phone contact after participants discontinue the study drug.

OS distributions will be compared in hierarchical testing order (order defined in Section 10.3.4) between treatment groups (nivolumab vs placebo) using a two-sided log-rank test stratified by AJCC T-Stage at Screening at the overall significance level of 5% (two-sided) in all randomized

participants. The hazard ratio and corresponding two-sided 100x (1-adjusted α)% CIs will be estimated using a Cox proportional hazards model, with treatment group as a single covariate, stratified by the above factors.

OS curves will be estimated using Kaplan-Meier (KM) product-limit methodology. Median OS with two-sided 95% CIs using the log-log transformation will be computed. In addition, OS rates at 6, 12, 18, 24, 30 and 36 months (and yearly after depending on follow-up) with two-sided 95% CIs using the log-log transformation will be computed.

Distant Metastasis-Free Survival (DMFS)

DMFS is defined as the time between the date of randomization and the date of first distant metastasis or date of death (whatever the cause), whichever occurs first.

Censoring rules for the analysis of DMFS are presented in Table 10.3.1.2-1.

Table 10.3.1.2-1:Censoring Scheme for Primary Definition of DMFS

| Situation | Date of Event or Censoring | Outcome |
|--|---|----------|
| Distant metastasis | Date of first distant metastasis | Event |
| Death without distant metastasis | Date of death | Event |
| No baseline disease assessment | Date of randomization | Censored |
| No on-study disease assessments and no death | Date of randomization | Censored |
| No distant metastasis and no death | Date of last evaluable disease assessment | Censored |

DMFS will be analyzed using similar analyses methods as for RFS. No multiplicity adjustment will be applied.

Investigator-Assessed Outcomes on Next-Line Therapies

PFS2 is defined as the time from randomization to recurrence/objective disease progression after the start of the next-line of systemic anti-cancer therapy, or to the start of a second next-line systemic therapy, or to death from any cause, whichever occurs first.

In case PFS2 cannot be reliably determined, we will analyze the time from randomization to end or discontinuation of next-line treatment, second objective disease progression, or death from any cause, whichever occurs first.

The hazard ratio and corresponding 95% confidence intervals (CIs) will be estimated using a Cox proportional hazards model, with treatment group as a single covariate.

Objective response rates and duration of treatment on next-line therapies will be summarized.

[figure not shown]

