| Fo evaluate investigator-assessed outcomes on next- ine therapies. | Objective response rates (if applicable) Duration of treatment on next-line therapies Progression-free survival through next-line therap (PFS2) is defined as the time from randomization t recurrence/objective disease progression after the start of the next-line of systemic anti-cancer therapy or to the start of a second next-line systemic therapy or to death from any cause, whichever occurs first. End-of-next-line-treatment: To be used for situation where PFS2 cannot be reliably determined. Even defined as end or discontinuation of next-line treatment, second objective disease progression, or death from any cause, whichever occurs first. |
| | |

Table 1:Objectives and Endpoints^a

| Objectives | Endpoints |
|--|--|
| | |
| | |
| | |
| | |
| | |
| | |
| To characterize the pharmacokinetics (PK) and explore exposure-response relationships with respect to safety and efficacy. | PK parameters and exposure metrics calculated from serum concentration-time data and characterization of exposure-response relationships |
| To characterize the immunogenicity of nivolumab. | Detection of anti-nivolumab antibodies |
| Abbreviations: AE, adverse events; | |
| | |
| | IgG, immunoglobulin G; |
| | non Terminology for Adverse Events; OS, overall survival |
| PFS2, progression-free survival through next line th | erapy; PK, pharmacokinetics; |
| | |
| Objectives and endpoints for participants entering th | e optional open-label nivolumab are very similar to blinde |

^a Objectives and endpoints for participants entering the optional open-label nivolumab are very similar to blinded nivolumab/placebo participants with some subtle differences in endpoints to account for the open-label non-randomized nature of treatment and for participants presenting with recurrent unresectable/metastatic disease in the event of recurrence.

[figure not shown]
Study Design:

In this study, participants with completely resected Stage IIB/C melanoma with no evidence of disease, will be randomized (2:1), stratified by T stage, to receive nivolumab (480 mg IV every 4 weeks), or nivolumab-matched placebo until recurrence, unacceptability toxicity, withdrawal of consent, or a maximum of 12 months from the first dose of study treatment, which occurs first.

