| | | | | treatment-related toxicity persists, or as clinically indicated. Laboratory toxicities (eg, suspected drug induced liver enzyme elevations) will be monitored during the follow- up phase, based on results from on-site/local labs, until all study drug related toxicities resolve, return to baseline, or are deemed irreversible. |
| Pregnancy Test | X | Х | | Serum or urine. ^b Pregnancy testing is only required at FU1 and FU2, unless increased frequency and duration is required per local regulations. |
| Review of Concomitant Medication | X | Х | | Long-term use of corticosteroids and other immune- modulating medications will be reported. ^b |
| | | | | |
| | | | | |

| Procedure | Follow-up Visit 1 ^a | Follow-up Visit 2 ^a | After Follow-up Visit 2 | Notes |
|----------------------|-----------------------------------|-----------------------------------|-------------------------------|--|
| Efficacy Assessments | | | | |
| Body Imaging | See note | | | Contrast-enhanced (CE) CT of the chest, CE CT/MRI of the abdomen/pelvis, and all other known and/or suspected sites of disease. Imaging of extremities for resected melanomas located in the extremities is not a requirement and may be conducted per local standard of care. Extremity imaging should be conducted in the event of a suspected locoregional relapse that is not clinically unequivocal. |
| | | | | For participants with Stage IIB/C melanoma (Nivo or Placebo blinded portion): |
| | | | | • Years 1, 2, and 3: Every 26 weeks (± 14 days) |
| | | | | • Years 4 and 5: Every 52 weeks (± 28 days) |
| | | | | • Participants who develop a loco-regional recurrence only, must be followed by surveillance imaging until the development of distant metastases. |
| | | | | • If a participant starts systemic anti-cancer therapy for melanoma recurrence after study drug discontinuation, other than optional open-label on- protocol nivolumab systemic therapy, or for a new non-melanoma tumor, follow-up scans can be done as per local standard of care. |
| | | | | For optional open-label nivolumab treatment after first recurrence: |
| | | | | ARM 1 (Resectable Disease) ^d |
| | | | | Participants enrolled with recurrent Stage III/IV resected disease |
| | | | | • Years 1, 2, and 3: Every 12 weeks (± 7 days) |
| | | | | • Years 4 and 5: Every 26 weeks (± 14 days) ^c |

Table 2-3: Long-Term Follow-Up CA20976K (Applies to All Participants: Blinded or Open-label Treatment)

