6.1.2 Inclusion Criteria for Participants Receiving Treatment after Recurrence

1) Signed Written Informed Consent

a) Participants must have signed and dated a separate IRB/IEC approved written informed consent form for open-label treatment with nivolumab monotherapy in accordance with regulatory and institutional guidelines. All other informed consent related details discussed in Section 6.1.1 for participants receiving blinded treatment apply to participants receiving treatment after recurrence.

2) Type of Participant and Target Disease Characteristics

- a) Participant must have been randomized, treated and have documented recurrence (per Section 9.1.2.1) of melanoma on blinded nivolumab or placebo treatment
- b) Recurrent disease must have been diagnosed within 3 years of last dose of blinded study. Participants assigned to blinded nivolumab treatment must have completed 1 year of therapy and have experienced disease recurrence more than 6 months following the last dose.
- c) Participant must not have received any other systemic anticancer therapy (including investigational anticancer therapy) or loco-regional anticancer therapy (other than surgery for complete resection of the recurrence and radiation therapy administered with a palliative intent) between the last dose of blinded study treatment and the first dose of open-label study treatment.

NOTE: Prior adjuvant radiation therapy (RT) after neurosurgical resection for central nervous system (CNS) lesions or prior RT to CNS metastases is allowed.

- d) Palliative/definitive radiotherapy, if administered, must have been completed at least 2 weeks prior to study drug administration
- e) Arm 1 (resectable disease only): Complete documented resection of recurrent disease (preferably within 12 weeks prior to assignment to open-label treatment) with margins negative (per local standard) for disease. For CNS lesion(s), documentation indicating that there has been complete resection of CNS lesion(s) will suffice as confirmation of negative margins.

NOTE: A copy of the de-identified pathology report(s) confirming negative margins on the resected specimen must be sent to the Central Laboratory vendor prior to assignment to open-label treatment.

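### After a loco-regional recurrence the scan interval depends on randomized arm, through open-label eligibility, and this can shift the DMFS hazard ratio modestly in favour of nivolumab

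*Combined protocol and SAP*

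**What the plan says.** **Imaging.** For the blinded portion, Table 2-3 sets body imaging at "Years 1, 2, and 3: Every 26 weeks (± 14 days"), then every 52 weeks in years 4 and 5. Participants with only a loco-regional recurrence continue surveillance scans until distant disease appears. Under Section 5.1.1, those who decline open-label treatment stay on this table. Once systemic therapy other than open-label nivolumab starts, scans may follow local practice, with no interval given. For open-label Arm 1 (resected recurrence) the table says "Years 1, 2, and 3: Every 12 weeks (± 7 days"), then every 26 weeks in years 4 and 5. Arm 1 also needs a disease-free scan in the 28 days before assignment (Section 6.1.2).

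**Entry to open-label treatment.** Section 6.1.2 applies one time limit to both arms: "Recurrent disease must have been diagnosed within 3 years of last dose of blinded study". It adds a condition for the nivolumab arm only, whose participants "must have completed 1 year of therapy and have experienced disease recurrence more than 6 months following the last dose".

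**Analysis.** DMFS runs from randomization to first distant metastasis or death, and the plan states: "DMFS will be analyzed using similar analyses methods as for RFS. No multiplicity adjustment will be applied". Table 10.3.1.2-1 does not censor DMFS at new anticancer therapy, whereas Table 10.3.1.1-1 does so for RFS. For the other endpoint that looks past recurrence, Section 10.3.1.2 says "PFS2 is defined as the time from randomization to recurrence/objective disease progression after the start of the next-line of systemic anti-cancer therapy" (start of a second next-line therapy and death also count).

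**The concern.** RFS ends at first recurrence, and until then both arms share one scan schedule. DMFS continues beyond that point. A participant who relapses locally may then be scanned every 12 weeks or every 26 weeks, and the rule deciding which depends on randomized arm. A metastasis is dated when it is found, so the arm scanned more often shows earlier events even if the disease behaves identically.

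Blinding does not help. Section 7.2.2 unblinds anyone who enters open-label treatment, and the eligibility rule itself refers to the assigned arm. A larger sample does not average the effect out either. At stake is the DMFS hazard ratio, a named secondary result that will be read as a treatment effect.

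**Working it through.** The plan gives no DMFS power or effect figure, so there is nothing to reproduce first.

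**1. Cut-off for nivolumab participants.** Dosing every 4 weeks for 12 months gives 13 doses, at weeks 0, 4, …, 48. Six months after the last dose is 48 + 26 = week 74, about month 17. The Synopsis counts from completion of 12 months, which gives about month 18. Nivolumab participants who did not complete 1 year are never eligible.

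**2. Detection delay.** If onset is uniform between scans, mean delay = interval / 2:
- 12-weekly: 6 weeks
- 26-weekly: 13 weeks, a gap of 13 − 6 = 7 weeks
- 52-weekly: 26 weeks, a gap of 26 − 6 = 20 weeks where 12-weekly Arm 1 scans run against it

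**3. Share of nivolumab recurrences barred by timing.** Assume 20% recurrence at week 104 and 30% at week 260 with piecewise constant hazard. These lie within the ranges in Section 3.2 (15% to 20% for IIB and 30% for IIC at 24 months; about 25% and 40% at 5 years).
- By week 74: 1 − 0.80^(74/104) = 14.7%
- By week 156: 1 − 0.80 × (0.70/0.80)^(52/156) = 23.5%
- Barred: 14.7/20 = 73% of recurrences up to week 104, and 14.7/23.5 = about 62.5% up to week 156

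**4. Effect on the hazard ratio.** Simulation with no true arm difference, 2:1 allocation and 2 million participants per scenario. The same draws were analysed with the protocol's arm-dependent schedule and with the blinded schedule for everyone. The factor is the ratio of the two log-rank hazard ratios (nivolumab/placebo), so a common schedule gives 1 by construction.

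Assumptions:
- 24-month relapse 15% or 30%
- first relapse loco-regional in 47% (the local/in-transit share for Stage IIB in Section 5.4.1) or 60% (assumed)
- median 12 or 36 months from loco-regional to distant disease
- open-label uptake 50% or 100%, starting 8 weeks after recurrence
- every distant metastasis found at a scheduled scan
- staggered follow-up

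| Uptake | Follow-up 8–30 months | Follow-up 24–48 months |
|---|---|---|
| 50% | 0.970–0.990 | 0.988–0.994 |
| 100% | 0.944–0.981 | 0.978–0.988 |

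Thirty of the 32 runs lie between 0.96 and 0.994. The two lowest (0.944 and 0.949) combine full uptake, 60% loco-regional first relapse, a 12-month median and short follow-up.

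**5. Local practice outside open-label treatment.** The same model was run with 25% relapse, 50% loco-regional, a 12-month median, full uptake and 24–48 months of follow-up. Everyone outside open-label treatment was scanned at one local interval:

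| Local interval (weeks) | 6 | 8 | 12 | 16 | 26 |
|---|---|---|---|---|---|
| Factor | 1.004 | 1.003 | 1.000 | 0.997 | 0.989 |

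The factor crosses 1 where the local interval equals the open-label one.

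**The case against.** The strongest objections, and what stands of each:

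- **The effect is small and the simulation is near its upper end.** Section 5.1.1 has 12-weekly physical examinations for a year after Follow-up Visit 2, and Sections 9.1.1 and 9.1.2.2 provide for unscheduled imaging on suspicion. Detection between scheduled scans shrinks the gap. This stands.
- **Open-label entry is not automatic on placebo.** It is optional and needs separate consent, resection with negative margins for Arm 1, ECOG 0 or 1, no other systemic therapy and no second recurrence (Sections 6.1.2 and 6.2.2). A reader might infer that every placebo recurrence moves to 12-weekly scans. The documents support only that timing within 3 years does not bar them.
- **The direction is not fixed.** A reader might infer that the bias must favour nivolumab. For participants on off-protocol systemic therapy it depends on an interval the documents do not give. Even on the 26-weekly schedule, cutting everyone at exactly 24 months, just after the week-104 scan, gives a simulated null hazard ratio of about 1.00 to 1.03. Staggered follow-up restores the direction shown above.
- **PFS2.** It is tempting to extend the argument to PFS2. Progression counts there only after next-line systemic therapy starts, and off-protocol therapy moves scans to local practice, so 26-weekly is not the comparator. No direction can be claimed.
- **The SAP may cover it.** Sections 10.3 and 10.3.3.6 defer detail to the SAP. The combined document as supplied contains no DMFS analysis that allows for unequal scan intervals. If one exists elsewhere, the point is met.

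**Conclusion.** The point holds for DMFS. Access to 12-weekly scans after a loco-regional recurrence depends on randomized arm, and the planned analysis dates events by detection without allowing for it. Where the 26-weekly schedule applies and follow-up is staggered, the spurious factor on the DMFS hazard ratio is about 0.96 to 0.99. At the most extreme assumptions it reaches 0.94, and it is nearer 0.98 to 0.99 with longer follow-up. These figures rest on assumed relapse rates, uptake and time to distant disease, and on scan-only detection. If local scans are 12-weekly or more frequent, the factor is about 1.00.

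PFS2 ascertainment also depends on the schedule after recurrence, but its direction is unknown. RFS and OS are unaffected. DMFS is secondary and outside the RFS–OS testing hierarchy, so this concerns how its estimate is read and not type I error. A shift of this size could matter to a borderline DMFS result. It could not by itself create a large one.

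**What to change.** In Section 10.3.1.2, add a DMFS sensitivity analysis that:
- treats each distant metastasis as interval-censored between the last scan free of distant disease and the first scan showing it
- enters deaths without distant metastasis at their exact date
- fits a proportional hazards model for interval-censored data, stratified by T-stage
- is reported beside the actual-date hazard ratio, without acting as a condition for describing a DMFS result

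Add a table of actual scan intervals after first recurrence by arm, split by open-label entry and off-protocol systemic therapy. It would show whether the imbalance occurred and what local practice was.

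Moving events to the next point on a common 26-week grid looks simpler but does not work. With the permitted ±14-day window, a scan one day late is pushed back about 26 weeks, and the factor stays at 0.97 to 0.99. With scans exactly on the grid it over-corrects to 1.00 to 1.03.

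The cost is SAP wording, one extra analysis and one table, from dates already collected. The interval-censored estimate will be slightly less precise. It is also not assumption-free, because the schedule changes at recurrence and recurrence itself predicts metastasis, so it should be read as a sensitivity analysis. No imaging, eligibility or treatment rule changes.
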